## **Methodology**

Prospective, Non-randomized, Interventional, Controlled

*The Biomedical Research Ethics Committee of Peking University First Hospital* is overseeing the research. ([contact]; Email: [[contact]](mailto:[contact]); Address: [name])

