## **Background**

Since 1992 when intersphincteric resection (ISR) for rectal cancer was first proposed by Braun et al, ISR has been widely used since it can significantly improve patients' quality of life by preserving the anus, especially for those with low rectal cancer. A series of studies have demonstrated its safety and feasibility. Standard laparoscopic ISR can not only ensure the radical resection of the tumor, but also preserve the anus.

Laparoscopic ISR with double stapling technique (DST) can provide a clearer view of the narrow pelvic and intersphincteric space, and the minimally invasive approach can relieve postoperative pain, shorten hospital stay, and generate better cosmetic outcomes compared with traditional combined abdominal perineal resection.

The wide application of ISR and DST has greatly improved the anal preservation rate for low rectal cancers, but the technical difficulty has also been obviously increased. In addition, for ultralow rectal cancers, because of the limited pelvic space, laparoscopic distal rectal transection could only be finished by multiple staplings resulting in an overlong stapling line, which could increase the risk for postoperative anastomotic leakage rate, which would seriously affect the patient's recovery and quality of life. Or the limited space could make it almost impossible to remove enough rectum to ensure a radical resection of the tumor, so distal rectal resection would have to be performed by converting to a transanal approach, that would definitely prolong the operative time and also increase the risk for anastomotic leakage. Although many scholars have tried to solve this problem, all the methods have failed to fundamentally solve the problem of "the oblique dissection" of the distal rectum for ultralow rectal cancers.

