## Objective

To confirm the safety, feasibility and advantages by comparing the perioperative variables, postoperative functional and oncological outcomes of patients with ultralow rectal cancer treated by laparoscopic traditional distal rectal dissection vs. by transanterior obturator nerve gateway approach.

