### ➤ Inclusion criteria

- 1) Age: 18-80 years old;
- 2) Pathologically diagnosed as rectal cancer with the lower margin of the tumor from the anal margin  $\leq 5$ cm;
- 3) CT, MRI or endoscopic ultrasonography: Single tumor, clinical T stage  $\leq 3$  or no invasion of the internal sphincter, maximum diameter  $\leq 10$ cm, no distant metastasis;
- 4) The patient or the patient-authorized representative completely understands the study protocol and voluntarily participates in this study, agrees to sign written informed consent.

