- 4) Urethral catheterization will be routinely done preoperatively
- 5) If the patient refuses to accept the novel approach before surgery, they will be directly enrolled in the traditional group. If both approaches are acceptable to the patient, the decision whether to use the novel approach will be made according to the intraoperative

conditions (see operating procedures below).

- Operating procedures

General anesthesia; Modified lithotomy position (Fig. 1a); Establishment of pneumoperitoneum: Place a trocar 1cm above the umbilicus through which to establish pneumoperitoneum and keep the abdominal pressure as 12 mmHg (millimeters of mercury).

Trocar placement: above the umbilicus (trocar C, 10 mm), upper right and left quadrants (trocars B and D, 5 mm), lower right quadrant (trocar A, 12 mm), lower left quadrant (trocar E, 5 mm), the midpoint between the pubic symphysis and umbilicus (trocar F, 5 mm).

[figure not shown]

Fig.1 Patient position and trocar placement

Abdominal exploration: Explore the abdominal cavity in accordance with the principle of non-contact, from far to near step by step, explore the tumor finally.

The mesosigmoid and mesorectum are dissected from the right lateral rectum towards the root of the inferior mesenteric artery (IMA). The IMA is transected and ligated, so is the inferior mesenteric vein. Posterior space of the descending colon is dissected following opening the peritoneum beside the left rectum. The rectum in the pelvis is mobilized from posterior rectal space, anterior rectal space to bilateral rectal space successively. The lower edge of the tumor is marked by a clamp. The linear stapler is placed in the pelvis to clamp the distal rectum below the tumor to see if the transection can be done more than 1cm from the lower edge of the tumor. If yes, the distal rectum will be transected by the traditional approach (that means the patient will be assigned to the traditional group). The proximal bowel is transected through a small midline incision. Then the coloanal

anastomosis will be done intracorporeally. A surgical drain is placed in the pelvis and a terminal ileostomy is routinely performed. All incisions are closed.

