### **Statistics**

IBM SPSS (Statistical Package for the Social Sciences) Statistics 25 (IBM, Inc., Armonk, NY) will be used to perform statistical analyses. The *t* test and Mann-Whitney *U* test were used for quantitative data between groups. Qualitative data were compared by  $\chi^2$  or

Fisher's exact test and survival distributions were analyzed by log-rank test.

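### Only unadjusted tests are planned, although refusal and an intraoperative 1 cm stapler test set the groups, so the leakage and survival comparisons are confounded and the plan does not say so

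*Combined protocol and SAP*

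**What the plan says.** Methodology describes the study as "Prospective, Non-randomized, Interventional, Controlled", and Trial sites adds that it is multi-centre. The Objective is comparative: "To confirm the safety, feasibility and advantages by comparing the perioperative variables, postoperative functional and oncological outcomes".

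Allocation is described under Treatment, in two steps.

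- Preoperative preparation, item 5: "If the patient refuses to accept the novel approach before surgery, they will be directly enrolled in the traditional group".
- Operating procedures, for patients who accept both approaches: the stapler is placed below the tumour to see whether transection is possible more than 1 cm from its lower edge. "If yes, the distal rectum will be transected by the traditional approach". If it is not possible, the novel approach is used and the patient belongs to the experimental group.

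The Statistics section then gives the entire analysis: the t test and Mann-Whitney U "test were used for quantitative data between groups. Qualitative data were compared by" chi-square or Fisher's exact test, and log-rank for survival. The documents contain no regression, weighting, matching, stratification, centre effect, balance check or sensitivity analysis, and no statement on confounding. Anastomotic leakage is among the Primary outcomes, as a crude rate per group. Survival appears under Follow-up, items 7 and 8.

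**The concern.** Among patients who accept both approaches, anatomy alone decides the group. By the protocol's own account that anatomy is prognostic. The Background explains that a narrow pelvis forces the surgeon to fire the stapler several times, "resulting in an overlong stapling line, which could increase the risk for postoperative anastomotic leakage rate". It also says that limited space hampers radical resection, which bears on the oncological outcomes. The rule therefore tends to send higher-risk patients to the experimental group. Refusal and centre may add bias in either direction.

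Crude tests pass these differences straight into the results. Through the stapler rule, the plausible errors are a false safety signal against the novel approach or a real benefit that is hidden. A false claim of advantage becomes less likely by this route. Two related points:

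- **Distal margin, angle and conversion** (all Primary outcomes). Accepting controls are selected on whether the stapler reaches far enough below the tumour, which is close to the distal margin itself. Angle and conversion depend on the same anatomy.
- **Functional scores** (lesser point). IIEF-5 is collected preoperatively in men but not used in the 1-year comparison. The preoperative Wexner score serves only for eligibility.

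ΔAngle is measured within patients of the experimental group, so this between-group confounding does not affect it.

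**Working it through.** **What the documents give.** Sample size states 100 experimental and at least 100 control cases, with no alpha, power, event rate or effect size, so that figure cannot be reproduced. For scale, at 100 v 100 and two-sided 5%, power for leakage would be 27% (10% v 5%), 41% (16% v 8%) or 66% (15% v 5%). All rates here and below are assumptions.

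**Model 1: a prognostic factor correlated with stapler difficulty.** X is standard normal and logit P(leak) = a + ln(1.5)·X, with a set to give 10% leakage overall. Stapler difficulty has correlation ρ with X. A share r refuses, independently of X. Acceptors above a difficulty cut-off receive the novel approach, with the cut-off set for equal groups: (1 − r) × P(above) = 0.5, so P(above) = 0.5/0.8 = 0.625 at r = 20%. The rejection rate is the exact sum, over all pairs of leak counts in 100 v 100, of the binomial probabilities of pairs where chi-square is significant. With no effect of approach:

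| ρ, refusal | Leakage, novel v traditional | Significant | Against novel | For novel |
|---|---|---|---|---|
| no confounding | 10.00% v 10.00% | 5.20% | 2.60% | 2.60% |
| 0.3, 20% | 10.64% v 9.36% | 6.25% | 5.01% | 1.25% |
| 0.5, 0% | 11.43% v 8.57% | 10.54% | 10.09% | 0.46% |
| 0.7, 0% | 12.00% v 8.00% | 15.84% | 15.63% | 0.20% |

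Fisher's test gives 3.6–10.6% instead of 2.9%.

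*Masked benefit* (odds ratio 0.3 for the novel approach):

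- No confounding: 3.26% v 10.00%, difference −6.7 points, shown in 49.0% of trials.
- ρ 0.3, 20% refusal: 3.49% v 9.36%, −5.9 points, shown in 39.4%.
- ρ 0.7, no refusal: 3.97% v 8.00%, −4.0 points, shown in 21.4%.

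**Model 2: the stapler result itself sets the risk.** Let f be the share failing the test. The share of test failures among controls is r·f / [r + (1 − r)(1 − f)]. With f = 50% and r = 20% this is 0.10/0.60 = 0.167. If failing doubles leakage (16% v 8%), the control rate is 0.833 × 8% + 0.167 × 16% = 9.3%, the crude risk ratio is 16/9.3 = 1.71, and the false-positive rate is 29%. Over refusal of 10–30% the rate is 25–35%. At 1.5 times the risk it is 11–14%; at 3 times, 62–79%.

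**Log-rank** (simulated; assumed 20% events by 3 years, hazard ratio 1.5 per SD, otherwise as Model 1). False positives are 6.9–29.0% instead of 5.1%, almost all against the novel approach.

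**What adjustment achieves for leakage** (simulated; overlap weights from six covariates plus 4–8 centres):

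- All confounding measured: false positives 4.7–6.3% with bias near 0, against 5.4–14.9% and 0.9–3.7 points crude. A true benefit is shown in 28–45% of trials, against 23–40% crude.
- Unmeasured part of stapler difficulty equally prognostic: 18–46% crude and still 9–27% weighted, against the novel approach.

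**Overlap on the stapler result.** Only refusers who would fail the test are comparable controls. Per 100 experimental patients there are 100·r·f / [(1 − r)·f] = 100·r/(1 − r) of them: about 11, 25 or 43 at refusal of 10%, 20% or 30%. Power for 16% v 8% would then be about 20%, 27% or 32%.

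**IIEF-5.** The shift in the 1-year difference is the pre-post correlation times the preoperative gap. A 2-point gap gives 0.6 to 1.4 points at correlations of 0.3 to 0.7.

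**The case against.** The strongest objection is that a propensity score does not reach the main problem. Acceptors have no overlap on the stapler result, the near-zero bias after weighting assumes that measured factors carry all the confounding, and an adjusted figure may look more credible than it is. This stands as a limit: even in the favourable case, weighting recovers only about 5 points of power. It is why the limitation statement is as necessary as the adjustment. It does not justify crude tests alone, which leave the measured part in as well.

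Second, the Background links limited space to leakage through repeated stapling or transanal conversion, which the novel approach is meant to change. That supports masked benefit more directly than a false safety signal. The point is fair, but whether the new approach changes stapling and leakage is what the study has to show. If it does not, the excess risk stays with the experimental group.

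Third, the sizes depend on assumptions, and the two models give different ranges. This stands, and only direction and order of magnitude should be taken from them. It also stands that survival is not a listed primary outcome, that a weighted Cox analysis was not simulated, and that ΔAngle comes only from test failures and is defined without a sign, so an interval excluding zero would not by itself show benefit.

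**Conclusion.** The concern holds and must be fixed. Followed as written, the plan gives a confounded comparison of a primary outcome and of survival, and it does not disclose this. That conclusion rests on the text alone: unadjusted tests, allocation by refusal and stapler reach, and the protocol's own link from pelvic space to leakage.

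The size cannot be computed from the documents. Under the assumptions shown, inflation runs from slight (6.3% at ρ 0.3 with 20% refusal) to serious (25–35% if failing the test doubles leakage), and the chance of showing a real benefit can fall by more than half. The direction from the stapler rule is against the novel approach; the direction from refusal and centre is unknown.

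**What to change.** **1. Adjusted analysis of leakage and survival (must).** Keep the crude tests. Before analysis, pre-specify one propensity score from age, sex, tumour distance from the anal verge as a value, maximum diameter, clinical T stage, neoadjuvant therapy, and centre where both approaches are used.

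- Overlap weights would serve, with a weighted risk difference for leakage and a weighted Cox model for survival, both with robust standard errors. Another single-score or penalised method is acceptable. About 20 leaks (10% of 200, assumed) cannot support seven or more ordinary outcome-model terms.
- State the target population (patients with baseline overlap), covariate balance and effective sample size per group.
- Report the number of patients at centres using one approach only and leave them out of the main adjusted analysis. Add a sensitivity analysis that includes them with centre left out of the score.

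**2. Limitation statement (must).** Say that baseline adjustment cannot remove confounding by the stapler result, and that overlap on it can come only from refusers. Record that result in refusers where available, and report how many refusers there are and how many met the 1 cm criterion. Report group differences in angle, distal margin and conversion as descriptive. Report ΔAngle as a within-patient estimate with a 95% CI.

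**3. Functional scores (should).** Compare 1-year IIEF-5 in men by ANCOVA on the preoperative score. Keep the preoperative Wexner score and adjust the post-closure scores for it.

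**Cost.** SAP text, analysis time and some record review; no new visits or patients. In the simulations, adjusted leakage intervals were 7–32% wider when uptake differed moderately between centres and 14–48% wider when it differed strongly, with an effective 44–88 patients per group. With one of five centres using the traditional approach only, they were 21–33% wider. The number of centres is not stated. For patients operated on since 2020-12-01, tumour distance, preoperative Wexner score and refusers' stapler results depend on existing records.

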To solve the problem above, on the basis of a large number of ISR-DST performing experience, [name], the director of this clinical trial has explored a new distal rectal resection method-- transanterior obturator nerve gateway approach. This approach can conspicuously expand the pelvic space and optimize the dissection angle without significantly prolonging the operative time, thus reducing the technical difficulty. So, by using this method, it would be more likely to preserve the anus and reduce the possibility of converting to transanal approach without breach of tumor's radical resection. The purpose of this clinical trial is to prospectively collect and compare data on the patients' perioperative items and postoperative functional and oncological outcomes of this novel approach with the traditional approach, so as to confirm the safety and feasibility of this novel approach and its advantages over the traditional approach.

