### **Sample size**

Two groups are designed, patients who are to receive the traditional approach to transect the distal rectum are assigned to the control group, patients who are to receive the transanterior obturator nerve gateway approach to transect the distal rectum are assigned to the experimental group. 100 cases are to be enrolled for the experimental group and not less than 100 cases are to be enrolled for the controlled group.

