### **Primary outcomes**

[figure not shown]
- The degree of Angle denotes the degree of angle between the linear stapler and the longitudinal axis of the rectum when transecting the distal rectum.
- The degree of  $\Delta$ Angle represents the degree of angle between the simulated stapling line with the total mesorectal excision approach and the real stapling line with the transanterior obturator nerve gateway approach (this outcome is measured only in patients of the experimental group).
- Length of distal resection margin indicates the shortest distance between the distal border of the tumor and the edge of the distal resection.
- Rate of conversion to transanal transection and anastomosis of the rectum: For each case, whether there is a conversion to transanal transection and anastomosis of the rectum during the operation will be recorded. The gross conversion rate (No. of cases undergoing conversion/total No. of cases enrolled \*100%) for each group will be calculated immediately after the last patient's surgery.
- Rate of anastomotic leakage: Whether the patient complicates with anastomotic leakage postoperatively will be followed up till 6 months after surgery. The gross anastomotic leakage rate (No. of cases diagnosed with anastomotic leakage/total No. of cases enrolled \*100%) for each group will be calculated 6 months after the last patient's surgery. Anastomotic leakage will be diagnosed if the patient has clinically apparent leakage signs (such as the emission of gas, pus, or feces from the pelvic drain, or peritonitis) or extravasation of endoluminally administered watersoluble contrast medium according to CT.

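### The aim is to confirm safety and advantages, but four unranked between-group primary outcomes get only difference tests, with no alpha, multiplicity control, success rule or interval

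*Combined protocol and SAP*

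**What the plan says.** Background gives the purpose as collecting and comparing data "so as to confirm the safety and feasibility of this novel approach and its advantages over the traditional approach". Objective repeats it: "To confirm the safety, feasibility and advantages by comparing the perioperative variables, postoperative functional and oncological outcomes".

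Primary outcomes lists five items without ranking them. One, ΔAngle, has no control-group counterpart: "this outcome is measured only in patients of the experimental group". That leaves four between-group outcomes: Angle, length of the distal margin, conversion to a transanal approach, and anastomotic leakage. For leakage, "Whether the patient complicates with anastomotic leakage postoperatively will be followed up till 6 months after surgery". For conversion and leakage the section adds only that a gross rate will be calculated in each group.

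Sample size says "100 cases are to be enrolled for the experimental group and not less than 100 cases are to be enrolled for the controlled group" and gives no basis for these numbers.

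Statistics names the software, the t test and Mann-Whitney U test, chi-square or Fisher's exact test ("test were used for quantitative data between groups. Qualitative data were compared by" these two), and the log-rank test. No section states an alpha, sidedness, a multiplicity procedure, a success rule, a safety margin or a confidence interval.

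**The concern.** A plan that sets out to confirm something should say beforehand which results would do so. Two gaps follow.

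- **Advantage.** With four unranked primaries, an advantage could mean any one significant result, a particular one, or all four. Under the first reading, the chance of a false claim can exceed that of a single test. Under the last, it cannot. The plan does not choose.
- **Harm.** Leakage is the only complication among the primary outcomes. Background presents it as a problem of existing technique (a long stapling line, "which could increase the risk for postoperative anastomotic leakage rate"), so a difference test suits a claim of benefit. But a difference test alone does not show how large an excess remains possible. At about 100 patients per group, that excess can be large even when p is above 0.05.

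**Working it through.** There is no figure of the plan's own to reproduce: the sample size comes without alpha, power, effect size or event rates.

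**Inputs.** From the documents: four between-group primaries; 100 experimental and at least 100 control patients. Assumed, because not given: two-sided 5% per test; control leakage of 5%, 10% or 15%.

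**1. False differences if any one result counts.** With k independent true nulls, the chance of at least one false difference is 1 − 0.95^k. In the direction favouring the new approach it is 1 − 0.975^k. The bounds k × 5% and k × 2.5% hold under any dependence.

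| True nulls | Any false difference | Bound | Favouring new approach | Bound |
|---|---|---|---|---|
| 1 | 5% | 5% | 2.5% | 2.5% |
| 2 | 9.75% | 10% | 4.9% | 5% |
| 3 | 14.3% | 15% | 7.3% | 7.5% |
| 4 | 18.5% | 20% | 9.6% | 10% |

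One or two true nulls is the more plausible range. Under Operating procedures, group depends on whether a margin above 1 cm can be reached, so equal distal margins are unlikely. The gateway is meant to allow a vertical transection, so equal Angles are unlikely too.

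**2. What a non-significant leakage test leaves open.** The test is the uncorrected chi-square. The interval is Newcombe's, for the risk difference d = p1 − p2 (experimental minus control), with Wilson limits l and u for each group:

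- lower = d − √[(p1 − l1)² + (u2 − p2)²]
- upper = d + √[(u1 − p1)² + (p2 − l2)²]

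Worked case, 12/100 versus 5/100: the pooled rate is 0.085, so z = 0.07/√(0.085 × 0.915 × 0.02) = 1.775 and p = 0.076. The Wilson limits are 7.00% to 19.81% and 2.15% to 11.18%. The upper limit is 7 + √(7.81² + 2.85²) = 15.3 points. The lower is 7 − √(5.00² + 6.18²) = −0.9 points.

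| Leaks per 100, experimental vs control | p | Newcombe 95% interval (points) |
|---|---|---|
| 12 vs 5 | 0.076 | −0.9 to +15.3 |
| 19 vs 10 | 0.071 | −0.9 to +18.9 |
| 26 vs 15 | 0.054 | −0.2 to +22.0 |
| 5 vs 5 | 1 | upper limit +6.8 |
| 10 vs 10 | 1 | upper limit +8.7 |
| 15 vs 15 | 1 | upper limit +10.1 |

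The first three rows are the largest non-significant excess at each control count.

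**3. Power to detect a doubling of leakage** from 5/10/15%, by exact enumeration of two binomials:

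- Chi-square: 27/52/73% with 100 controls and 38/66/85% with 200.
- Fisher: 19/44/67% with 100 controls and 34/62/83% with 200.

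**4. Test and interval can disagree.** For 13 versus 5 per 100, chi-square p = 0.048 but the Newcombe interval is −0.1 to +16.5 points. A harm rule must therefore say which of the two governs.

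**The case against.** The strongest reply is that the inflation is conditional and modest. It needs a rule that any one result counts, which the documents never state. A reader might infer that the plan carries an 18.5% false-claim rate. The documents do not support that: the figure also needs four independent true nulls, which the allocation rule makes unlikely. This stands, and the lower range is the one to use.

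A reader might also infer that the sponsor will treat a non-significant leakage test as proof of safety, or that leakage is the safety criterion. Neither is written. Objective covers perioperative, functional and oncological outcomes, and the plan also records ileus, infection, urinary, sexual and anal function, and survival. Leakage alone therefore cannot carry a statement about overall safety. This stands too. It narrows the point to what a leakage p-value can show about leakage.

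Per-group rates will be calculated, so a reader could derive an interval from the counts. That makes the missing interval a smaller gap, but it does not say what the interval will be used for.

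Finally, allocation by achievable margin or by patient refusal is the larger problem, and controlling alpha does nothing about it. This is correct, and it limits what the change can achieve. It does not justify leaving the decision rules unwritten.

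**Conclusion.** The concern holds in a limited form. The omission is certain on the text: Statistics reads as complete, and no other section supplies the missing items.

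Its size is less certain. For advantage claims, the chance of a false difference is 5% to 9.75% with one or two true nulls (2.5% to 4.9% favouring the new approach), assuming two-sided 5% per test and that any one result counts. For leakage at 100 per group, non-significant results can leave excesses of +15.3 to +22.0 points unexcluded. Equal counts of 5 to 15 still leave +6.8 to +10.1. These leakage figures rest on assumed control counts.

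The change should be made, but the point ranks no higher than that. One should not infer that alpha control would make the comparison confirmatory: with this allocation, an adjusted p-value alone would still not confirm an advantage.

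**What to change.** Add to Statistics, before analysis:

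1. A two-sided overall alpha of 5%, with Holm's procedure across Angle, distal margin, conversion and leakage for any claim of advantage. One named primary outcome or a fixed testing order would also serve. Report ΔAngle outside this family, as an estimate with a 95% confidence interval.
2. The leakage risk difference (experimental minus control), always reported with an unadjusted Newcombe 95% interval. Base the harm statement on that interval alone. If it lies wholly above zero, report an excess. If it includes zero, report the upper limit as the excess not excluded, whatever the chi-square or Fisher p-value (this settles 13 versus 5). Claim a leakage benefit only if the Holm-controlled test rejects.
3. A statement that p>0.05 is not evidence of safety, and that the interval speaks to leakage only. Report the other recorded complications and functional outcomes alongside it.

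**Cost.** Wording only, with no new patients or data. Single advantage claims lose power: for leakage halved from 10% to 5% with 100 per group, power is 27% at 0.05 but 17%, 14% and 11% at Holm's 0.025, 0.0167 and 0.0125 steps. A single named primary, or the first outcome in a fixed order, keeps 0.05. Leaving harm outside Holm preserves its detection. For a doubling from 5/10/15% with 100 controls, the unadjusted interval lies wholly above zero in 24/51/72% of trials, against 9/29/52% at the 98.75% level. The confounding from allocation needs separate treatment.
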